8.2 EFFICACY ASSESSMENTS

Continuous Glucose Monitoring (CGM)

Starting at Visit 2, participants with T1DM will wear a blinded continuous glucose monitor (CGM) for the duration of the study as a safety measure for glucose levels.

Healthy volunteers will wear the CGM for the 10 days preceding and including the clamps.

The CGM will be placed by a member of the study team (unless the participants is familiar and prefers to do it on their own), participants will be instructed on the use and removal of the device, as well as reinsertion of the device as needed. During CGM wear, participants will be instructed to perform standard fingerstick glucose measurements and/or continue with personal CGM to manage their blood glucose. Participants will be encouraged to document their blood glucose levels and insulin coverage on a home Glucose/Insulin log, for review by the medical study staff. The FDA-approved system (Dexcom) includes a sensor and transmitter. It measures interstitial fluid glucose levels in the range of 40 mg/dl to 400 mg/dl every 5 minutes.

Standardized meal test

Upon admission to the TRI or ProSciento, the participants will have an intravenous catheter inserted and afterwards will receive a standard mixed meal challenge of consistent composition and calorie amount on both admissions. The meal will comprise 25% of daily calorie requirement with a 48-50% Kcal from carbohydrate, 35% from fat and 15-17% from proteins. The meal will be preceded by a pre-prandial dose of insulin calculated based on the participant insulin to carbohydrate ratio. 15 minutes prior to the start of the meal, a baseline sample will be drawn. From the start of meal, for the next 3.5 hours, at 30-minute intervals, blood samples will be obtained for glucose, glucagon, total GLP-1 and total GIP, and the study drug plasma levels (PK). The key objective of this meal study is to examine fasting and prandial glucagon responses while on GPR119 agonist treatment.

ECG will be performed during the meal test at the time of predicted drug concentration peak, 180 minutes, ± 5 minutes window, after taking the medication.

Euglycemic and hypoglycemic clamp procedures

At approximately 6 a.m., a primed, continuous infusion of [6,6] di-deuterated glucose will be started to enable determination of hepatic glucose production (HGP) and systemic glucose utilization via the glucose isotope dilution method; at least 2.5 hours will be allowed for isotope equilibration. The principal target of glucagon action is the liver, and HGP more specifically, and assessing this parameter will give physiological context to any observed changes in glucagon secretion during induced hypoglycemia.

At about 6 a.m. T1DM subjects will take the final dose of the study medication. A catheter will be placed in a vein on contralateral hand or arm and the arm warmed (via heating box or warming pad) to achieve "arterialization" of blood samples. Around 8:30am, shortly before the clamp insulin infusion start, the overnight insulin infusion will be discontinued. The euglycemic portion of the clamp will commence with insulin infusion at a constant rate of 25 mU/min-m². Blood / plasma glucose will be measured every 5 minutes and allowed to decrease until it reaches a value of approximately 90 mg/dl, at which point a 20% dextrose (D20) spiked with [6,6] di-deuterated glucose will be given (glucose infusion rate; GINF), at an adjustable rate, in order to maintain blood glucose at approximately 85 mg/dl. At approximately 9:30 a.m. (or following at least 15 minutes of stable euglycemia, operationally defined as 85 ± 10 mg/dl, 3 sets of blood samples at 10 min intervals will be obtained for glucagon, insulin, catecholamines, cortisol, growth hormone, GLP-1 and GIP, and glucose enrichment.

Subsequent to the 3rd baseline sample, the GINF will be stopped, the 25 mU/min-m² insulin infusion will be continued, and the hypoglycemic portion of the clamp study will begin. Blood glucose will be allowed to decrease over ~ 30 min until values of 50 to 55 mg/dl are observed and then will be maintained at this level for approximately 30 minutes by infusion of D20. Mild fluctuation of blood glucose values during the hypoglycemic portion of the clamp can be expected. As the blood glucose values approach the target level of hypoglycemia, an adjustable rate GINF infusion can be started at a low rate to prevent overshoot into more severe hypoglycemia and GINF adjusted as needed to maintain the target level of hypoglycemia. Blood sampling for glucose will occur every 5 minutes and at every 10 minutes for a panel of hormones and metabolite determinations (as described above). A questionnaire will be administered during the study to quantitate autonomic symptoms as the sum of scores ranging from 0 (none) to 5 (severe) for each of the following symptoms: anxiety, palpitations, sweating, tremor, hunger, and tingling.

After 30 minutes of sustained hypoglycemia, the insulin infusion will be discontinued, and the recovery phase of the clamp will start. Including the time needed to reach hypoglycemia (induction), it is estimated that this hypoglycemic phase of the clamp will be approximately 60 minutes. The time to recover to euglycemia (operationally defined as a target blood glucose of 85 ± 5 mg/dL) will be ascertained. Once insulin infusion has been stopped, to prevent potential further decline in plasma glucose, GINF will initially be continued, at least until plasma glucose has risen above 70 mg/dl, at which point GINF will be rapidly tapered and discontinued over the next 10 minutes. GINF will not be re-instituted unless plasma glucose declines again into the range of 50 mg/dl. In situations where blood glucose values decrease remain less than 50 mg/dl, at any time during the recovery phase, additional glucose will be given as a safety measure. Blood samples for glucagon, counter-regulatory hormones and glucose enrichment will be obtained every 10 minutes for 30 minutes, then every 30 minutes during the recovery period. The recovery phase of the study will continue until one hour into recovery, at which point a meal will be provided, and blood glucose values monitored until euglycemic values are attained.

Samples for PK studies will also be obtained.

Efficacy laboratory measures

During the standardized meal test the following will be measured:

Mixed Meal Tolerance (MMT)									
Time (min)	-15	-1	30	60	90	120	150	180	210
Glucose	x	x	x	x	x	x	x	x	x
Glucagon	x	x	x	x	x	x	x	x	
GLP-1	x	x	x	x	x	x	x	x	
GIP	x	x	x	x	x	x	x	x	
GPR119PK		x	x	x	x		x		x

Table 2

During the clamp studies, samples for blood / plasma glucose will be measured with an automated glucose analyzer and recorded on the study flow sheet, along with the rate of GINF at 5-minute intervals. All the other samples, per the flow sheet, will be collected, placed on ice at the time of collection and after centrifugation by study staff, aliquots will be frozen at -80° until analyses.

	Hyperinsulinemic euglycemic and hypoglycemic glucose clamp																				
	Baseline	Prior to Insulin infusion				Euglycemic phase					Euglycemic Steady state (maintenance)			Transition from Euglycemic to Hypoglycemic phase		Hypoglycemic phase steady state (maintenance)			Recovery phase		
Sample nomenclature	Baseline Lab Draws	-150	-20	-10	0	10	20	30	40	50	E10 min	E20 min	E30 min	T15 min		H10 min	H20 min	H30 min	R30 min	R60 min	
Time (min)*	Prior to -150	-150 Start Glucose Test	-20	-10	0	10	20	30	40	50	60	70	80		100		120	130	140	170	200
Glucagon			x	x	x	x	x	x	x	x	x	x	x		x	x	x	x	x	x	
Insulin			x	x	x	x	x	x	x	x	x	x	x		x	x	x	x	x	x	
Glucose enrichment	x		x	x	x						x	x	x			x	x	x	x	x	x
Catechola mines			x		x			x			x	x	x			x	x	x	x	x	x
Cortisol			x		x			x			x					x	x	x	x	x	x
Growth Hormone			x		x			x			x					x	x	x	x	x	x
GLP-1, GIP			x		x			x			x	x	x			x		x	x	x	x
GPR119 PK	x				x						x					x					x
Exosome					x						x						x		x	x	x
FFA			x		x			x			x	x	x		x	x	x	x	x	x	
Archive					x						x						x		x	x	x

Table 3

*Time 0 corresponds to the CLAMP insulin 25 infusion start

Glucagon and other hormone assays will be done using the paired samples from the two studies performed in each T1DM subject to reduce inter-assay variations. Because it has long been recognized that glucagon assays can be difficult, and can have relatively high levels of non-specific background, particular care will be made to select the most accurate available glucagon assay(s), and depending upon sample requirements, to run these in duplicate or triplicate.

PK determinations of study drug concentrations will be done by the pharmaceutical partner.

Additional plasma samples obtained during the clamp (baseline, end of euglycemic clamp, end of hypoglycemic phase, end of recovery) will be archived.

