To evaluate the effects of MBX-2982 upon fasting and postprandial glucagon, GLP-1 and GIP concentrations in subjects with T1D relative to placebo treatment.	Fasting and post-prandial levels of glucagon, GLP-1 and GIP
To evaluate the effects of MBX-2982 on patterns of glycemia determined by continuous glucose monitoring in subjects with T1DM relative to placebo.	Continuous glucose monitoring (CGM) indices of glycemic control including hypoglycemia (percent of time < 70 mg/dL, < 54 mg/dL), hypoglycemic events, mean glucose, percent of time 70-180 mg/dL, percent of time > 180 mg/dL, percent of time > 250 mg/dL, glycemic variability
To evaluate the pharmacokinetic profile of MBX-2982 in subjects with T1DM.	MBX-2982 plasma levels.

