On the morning of admission, subjects with T1DM will be instructed to withhold long-acting insulin injections, and not to eat breakfast (which will be served at the research center after admission). A T1DM subject will be asked to monitor blood glucose every four hours (or more frequently) and administer short-acting insulin to control hyperglycemia. The study physician and nurse will help guide subjects in these dose selections. Subjects who are on insulin pump therapy will continue their usual basal rates and prandial dosing of insulin delivery since this will clear rapidly once discontinued.

Upon admission to the Research Center, the participant will have an intravenous catheter inserted and afterwards will receive a standard mixed meal challenge of consistent composition and calorie amount on both admissions, preceded by a pre-prandial dose of insulin. The intervention drug will be taken 30 minutes, \pm 5 minutes window, after beginning the meal. At 30-minute intervals, preceding and during the meal, for the next 3.5 hours, blood samples will be obtained according to Table 2. The key objective of this meal study is to examine fasting and prandial glucagon responses while on GPR119 agonist treatment. After the mixed meal challenge, the IV catheter will be maintained. Subjects will receive a weight maintaining, controlled carbohydrate lunch and dinner on the unit. After dinner, research subjects will be kept NPO (other than water) and will remain fasting in the morning and until completion of the clamp study.

For T1DM subjects, a second catheter might be placed for an overnight infusion of low-dose regular insulin to control plasma glucose within a range of 80 to 120 mg/dl. A POC and/or CGM instrument will be used for bed-side glucose determinations. To monitor plasma glucose overnight, every 1 to 2 hours (more frequently if necessary). Blood glucose sampling/evaluation via CGM/POC will be done to inform adjustments of the insulin infusion rate using a previously established algorithm. No further subcutaneous insulin use, by injection or via pump delivery, will be used until subjects resume their usual therapy after the clamp study. The last medication dose will be taken before the beginning of the clamp.

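### Meal-test PK sampling puts one of six draws at the moment of dosing and none after the predicted 180-minute peak, so a fed peak at or after that time cannot be confirmed

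*Combined protocol and SAP*

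**What the plan says.** **Dosing.** On the meal-test day (Section 8.1.6, Visit 5; Visit 8 is identical), "The intervention drug will be taken 30 minutes", with a window of 5 minutes either way, after the meal begins.

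**ECG.** Section 8.2: "ECG will be performed during the meal test at the time of predicted drug concentration peak, 180 minutes", again with a 5-minute window, counted from the dose. Section 2.3.3.2 explains that the timed ECG responds to an in vitro QT signal.

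**PK draws.** The meal-test table in Section 8.2 is labelled Table 2, as is an unrelated table in Section 2.2.6.1. Its clock starts at the meal: "Time (min) -15 -1 30 60 90 120 150 180 210". The PK row, "GPR119PK x x x x x x", has six marks, which align with -1, 30, 60, 90, 150 and 210 minutes.

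**Narrative.** The Section 8.2 text reads differently: "From the start of meal, for the next 3.5 hours, at 30-minute intervals, blood samples will be obtained", and it includes drug levels among the analytes. Section 8.1.6 defers to Table 2.

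**Catheter.** Section 8.1.6: "After the mixed meal challenge, the IV catheter will be maintained".

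**Purpose.** The exploratory objective in Section 3 is "To evaluate the pharmacokinetic profile of MBX-2982 in subjects with T1DM". Its endpoint is simply plasma levels of the drug.

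**The concern.** Table 2 runs on the meal clock and the ECG on the dose clock. Read on the meal clock, the 210-minute draw looks like a post-peak sample. Shifted by the 30 minutes between meal and dose, it falls on the predicted peak itself, and the 30-minute draw falls at the moment of swallowing.

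Two things depend on this. A PK profile after a fed dose needs at least one sample on the way down to show that a peak has passed. And Visits 5 and 8 are the only visits at which the ECG is timed to the dose; each T1DM participant is on active drug at just one of them. If the prediction is right, or errs early, the highest concentration will be the last one drawn. The data then cannot show whether that ECG was at the peak or before it.

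**Working it through.** **1. Convert to the dose clock.** Post-dose time = meal-clock time minus dosing time.

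| Meal clock (min) | -1 | 30 | 60 | 90 | 150 | 210 |
|---|---|---|---|---|---|---|
| Dose at 30 | -31 | 0 | 30 | 60 | 120 | 180 |
| Dose at 25 | -26 | 5 | 35 | 65 | 125 | 185 |
| Dose at 35 | -36 | -5 | 25 | 55 | 115 | 175 |

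The ECG is at 30 + 180 = 210 minutes on the meal clock, the same time as the last draw. One of six draws (17%) is within 5 minutes of dosing, and none is beyond the predicted peak apart from window slack. The narrative schedule also stops at 3.5 h = 210 minutes, so following the text instead of the table would not add a later sample.

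**2. What comes next.** The next PK draw is the clamp-day baseline, just before the dose at about 6 a.m. (Section 8.2, Table 3). The documents give no clock time for the meal, so the exact gap cannot be stated. With that dose at about -150 minutes on the clamp clock, the later Table 3 draws (0, 60, about 110-120 and 200 minutes) reach about 150, 210, 260-270 and 350 minutes post-dose. They follow a fasted dose, and Section 2.2.7 reports significantly higher exposure with food.

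**3. The 180-minute prediction.** It cannot be reproduced: the documents give no Tmax for the 600 mg HCl salt taken with food. The only Tmax values (Section 2.2.6, Table 1) are 4.1, 1.7 and 3.0, for micronized free base at 100, 300 and 1000 mg, with no unit printed. Taken as hours, they average (4.1 + 1.7 + 3.0)/3 = 2.93 h, or 176 minutes. That is compatible with 180, no more. One value exceeds the last draw and one equals it.

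**4. How much is lost.** Assumed model: one compartment, oral, steady state, τ = 24 h, no lag, with

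C(t) ∝ exp(-ke·t)/(1 - exp(-ke·τ)) - exp(-ka·t)/(1 - exp(-ka·τ)),

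where ke = ln 2/half-life and ka is solved to give the stated Tmax. Half-lives are the extremes in Table 1, 18.4 and 29.1, taken as hours, so ke = 0.0377 and 0.0238 per hour. The last column is the proposed later draw. Each cell gives the fraction of Cmax for half-life 18.4 / 29.1.

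| True Tmax (h) | At 120 min | At 180 min | At 360 min |
|---|---|---|---|
| 1.7 | 0.997 / 0.998 | 0.968 / 0.980 | 0.866 / 0.913 |
| 2.4 | 0.995 / 0.997 | 0.993 / 0.995 | 0.899 / 0.934 |
| 2.5 | 0.993 / 0.995 | 0.995 / 0.997 | 0.904 / 0.937 |
| 3.0 | 0.975 / 0.983 | 1.000 / 1.000 | 0.928 / 0.953 |
| 4.1 | 0.923 / 0.947 | 0.983 / 0.989 | 0.973 / 0.982 |

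Under the present schedule the peak is bracketed (the highest sample is not the last) only up to a true Tmax of about 2.44 h. A 0.5 h absorption lag moves this to 2.42 h and lowers the smallest 180-minute fraction to 0.963.

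**5. Where a later draw would help.** With the redundant draw moved later, the bracketing limit is:

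| Last draw post-dose | Meal clock | Limit on true Tmax |
|---|---|---|
| 240 min | 270 min | 3.46 h |
| 300 min | 330 min | 3.88-3.89 h |
| 360 min | 390 min | 4.28 h |

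Only the 360-minute draw covers the Table 1 range up to 4.1 h (with the 0.5 h lag its limit is about 4.23 h). These limits ignore assay error. Near each limit the two samples differ by about 1% or less, so in practice the limits are somewhat optimistic.

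**The case against.** The strongest reply is that little is at stake. The protocol promises plasma levels, not Cmax, Tmax or AUC; the meal test's stated key aim is glucagon; and PK is exploratory. The modelled curve is so flat that an ECG at 180 minutes is close to peak exposure wherever the peak lies between 1.7 and 4.1 h. ECGs are also done at Visits 4 and 7, and the QT withdrawal rule in Section 7.2.1 uses QTcF, not concentration. Section 2.2.6.1 lists a completed fed-and-fasted PK study that included the HCl salt at 600 mg. All of this stands, and it sets the priority. It does not make the dosing-time draw useful, and the Tmax from that earlier study is not shown here.

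A reader might infer something stronger: that the fed peak cannot be identified at all, that the ECG timing cannot be checked, or that Cmax is badly truncated. The documents do not support that. A peak clearly before 180 minutes would appear as a fall from the 120- to the 180-minute sample. The last draw coincides with the ECG, so concentration at the ECG is known. The Cmax shortfall in the model is a few percent at most. The clamp-day samples do extend past 180 minutes, but they do not fill the fed-dose gap.

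**Conclusion.** The concern holds in a limited form. The 30-minute PK draw repeats the trough, and no fed-dose draw follows the predicted peak until the next morning. A peak at or after 180 minutes therefore cannot be told from a still-rising curve, and the Visit 5 and 8 ECGs cannot be confirmed as peak-timed. The loss is mainly in Tmax and in confirming the peak; the 180-minute sample is about 97-100% of Cmax for Tmax 1.7-4.1 h.

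The sampling times follow from the documents alone. The sizes rest on a one-compartment model and on free-base values, assumed to be in hours and carried over to a 600 mg fed dose of the HCl salt. If the salt's fed Tmax lies outside that range, the sizes change but the schedule's gap does not. Low priority.

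**What to change.** In Table 2 of Section 8.2, move the 30-minute GPR119 PK tube to about 390 minutes from meal start (6 h post-dose), at both Visit 5 and Visit 8 so that blinding is unaffected. A draw at 330 minutes would not be enough, since its limit of about 3.9 h falls short of the 4.1 h in Table 1. Keep the -1 draw as the single pre-dose value and the 210-minute draw paired with the ECG. In the same edit, make the Section 8.2 text, which implies PK every 30 minutes, agree with the table, and add a post-dose time row so that the two clocks cannot be confused.

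Cost: one table edit and one draw outside the meal-test window, around the unit lunch, through the catheter already kept in place. The number of tubes and the blood volume do not change. The added point brackets a later peak but locates Tmax only coarsely, because the last three draws would be at 2, 3 and 6 h.

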9 SAFETY AND OTHER ASSESSMENTS

Medical History and Physical Exam

A Health History will be obtained. A standard physical examination will be performed by a study physician, physician assistant, or nurse practitioner.

Physical exam will include general status, skin, HEENT (including fundoscopic examination), neck, cardiovascular, lungs, abdomen, upper and lower extremities, neurological, musculoskeletal and psychiatric systems.

Anthropometric Measures

Body weight (calibrated scale), height, will be obtained while in a gown, without shoes. BMI will be calculated.

Screening Labs

The laboratory assessments will be used to confirm study eligibility (inclusion/exclusion criteria), as well as overall health status:

- complete blood count (CBC) white blood count, red blood count, Hemoglobin, Hematocrit, MCV, MCH, MCHC, RDW, Platelet Count, MPV, Neutrophils, Lymphocytes, Monocytes, Eosinophils, Basophils, Abs Neutrophil Count, Abs Lymphocyte Count, Abs Monocyte Count, Abs Eosinophil Count, Abs Basophil Count
- comprehensive metabolic panel (CMP) (Anion Gap, Albumin, Globulin, A/G Ratio, Alkaline Phosphatase, ALT, AST, Bilirubin Total, BUN, Creatinine, eGFR by CKD-EPI, Calcium, Chloride, CO₂, Creatinine, Glucose, Potassium, Sodium, Total Protein)
- HbA1C
- lipid panel (Total Cholesterol, HDL, LDL, Chol/HDL ratio, LDL/HDL Ratio, Non-HDL Cholesterol, Triglycerides, VLDL, CHD Risk Assessment)
- thyroid function test: thyroid stimulating hormone (TSH) and free T4
- C-peptide (requires a blood glucose \geq 90mg/dL to be accurate)
- islet autoantibody panel (anti GAD Ab, anti IA-2 Ab, Anti ZnT8 Ab)
- Hepatitis B and Hepatitis C antibody tests [Hepatitis B Surface Antigen (HBsAg), Hepatitis B Surface Antibody (HBsAb), Hepatitis C Surface Antibody (HCsAB)]
- HIV 1 & 2 Ag/Ab Screening
- urinalysis
- Urine toxicology screening test (Amphetamine, Barbiturate, Benzodiazepine, Cocaine, Methadone, Opiate, THC, Tricyclics, Oxycodone)

- Serum Beta HCG for pregnancy in female subjects of childbearing potential

Screening labs can be repeated per PI discretion.

Follow up labs

- Complete blood count (CBC) white blood count, red blood count, Hemoglobin, Hematocrit, MCV, MCH, MCHC, RDW, Platelet Count, MPV, Neutrophils, Lymphocytes, Monocytes, Eosinophils, Basophils, Abs Neutrophil Count, Abs Lymphocyte Count, Abs Monocyte Count, Abs Eosinophil Count, Abs Basophil Count
- Comprehensive metabolic panel (CMP) (Anion Gap, Albumin, Globulin, A/G Ratio, Alkaline Phosphatase, ALT, AST, Bilirubin Total, BUN, Creatinine, eGFR by CKD-EPI, Calcium, Chloride, CO₂, Creatinine, Glucose, Potassium, Sodium, Total Protein)
- HbA1C
- lipid panel (Total Cholesterol, HDL, LDL, Chol/HDL ratio, LDL/HDL Ratio, Non-HDL Cholesterol, Triglycerides, VLDL, CHD Risk Assessment)
- Thyroid function test: thyroid stimulating hormone (TSH) and free T4• urine pregnancy test, for female subjects of childbearing potential

The **total amount of blood** required for the study will be about 547.1 ml during the whole study.

Vital Sign Measurements

Measurement of vital signs will include heart rate (HR), blood pressure (BP), respirations and temperature will be measured sitting for at least 5 min.

Electrocardiograms (ECGs): ECG will be done at screening and during intervention periods at visits 4 and 5, and visits 7 and 8. At visits 5 and 8, the ECG will be performed during the meal test at the time of predicted drug concentration peak 180 min after taking the medication. The QTcF will be manually calculated for each ECG.

Fingerstick glucose and ketone measures

Fingerstick glucose and/or monitoring of personal CGM will be encouraged to measure/monitor at home by the participant before meals and at bedtime.

Participants will be instructed to check urinary ketones and in case of symptoms indicative of ketoacidosis or blood glucose >250 mg/dl.

Counseling procedures and Insulin dose adjustments

The participants will be instructed to check their blood glucose with a glucometer/personal CGM device before each meal and at bedtime. The participants may be instructed on insulin dose adjustments, ketone testing and sick day management, hypoglycemia symptoms and treatment.

Assessment of adverse events. See below.

